6.6. Duration of Study

Patients are considered on study from the date of enrollment until initiation of post-olaparib therapy or for 30 days after removal from trial for any adverse event to allow for safety monitoring. Secondary efficacy endpoints will be tracked.

7. DOSING DELAYS/DOSE MODIFICATIONS

Any patient who receives treatment on this protocol will be evaluable for toxicity. Each patient will be assessed for the development of toxicity. Toxicity will be assessed according to the NCI Common Terminology Criteria for Adverse Events (CTCAE), version 5, and the NCI Patient Reported Outcomes-Common Terminology Criteria for Adverse Events (PRO-CTCAE).

Toxicity/Grade	Dose Adjustment and Management
·	Recommendations
Anemia (Hemoglobin)	
Grade 1 (\geq 10.0 – LLN g/dL)	No dose adjustment required.
Grade 2 (≥8.0 – <10.0 g/dL)	No dose adjustment required.
Grade 3 (<8.0 g/dL)	Dose interruption until recovery to grade ≤ 1 .
	Monitor hemoglobin weekly until recovery.
	If resolves to grade ≤ 1 within 28 days, resume at reduced dose 250 mg PO BID.
	Dose may be reduced to 200 mg PO BID if recurs at
	reduced dose, but if recurs for a third time, treatment
	should be discontinued.
Grade 4 Life-threatening	Dose interruption until recovery to grade ≤ 1 .
consequences; urgent intervention	Monitor hemoglobin weekly until recovery.
indicated	If resolves to grade ≤ 1 within 28 days, resume at reduced dose 250 mg PO BID.
	Dose may be reduced to 200 mg PO BID if recurs at
	reduced dose, but if recurs for a third time, treatment
	should be discontinued.
Thrombocytopenia	
Grade 1 (≥75 x 10 ⁹ /L)	No dose adjustment required.
Grade 2 ($\geq 50 \times 10^9/L - <75 \times 10^9/L$)	Dose interruption until recovery to grade ≤ 1 .
	Monitor platelets weekly until recovery.
	If resolves to grade ≤ 1 within 28 days, resume at reduced dose 250 mg PO BID.

7.1. Hematologic Toxicity

	Dose may be reduced to 200 mg PO BID if recurs at reduced dose, but if recurs for a third time, treatment
	should be discontinued.
Grade 3 (≥25 x 10 ⁹ /L - <50 x 10 ⁹ /L)	Dose interruption until recovery to grade ≤ 1 .
	Monitor platelets weekly until recovery.
	If resolves to grade ≤ 1 within 28 days, resume at reduced
	dose 250 mg PO BID.
	Dose may be reduced to 200 mg PO BID if recurs at
	reduced dose, but if recurs for a third time, treatment
	should be discontinued.
Grade 4 (<25 x 10 ⁹ /L)	Dose interruption until recovery to grade ≤ 1
	Monitor platelets weekly until recovery.
	If resolves to grade ≤ 1 within 28 days, resume at reduced
	dose 250 mg PO BID.
	Dose may be reduced to 200 mg PO BID if recurs at reduced dose, but if recurs for a third time, treatment
	should be discontinued.
Absolute neutrophil count (ANC)	should be discontinued.
Grade 1 (\geq 1.5 x 10 ⁹ /L)	No dose adjustment required.
Grade 2 ($\geq 1.0 - \langle 1.5 \times 10^{9}/L \rangle$)	No dose adjustment required.
Grade 3 ($\geq 0.5 - <1.0 \times 10^{9}/L$)	Dose interruption until recovery to $\geq 1.0 \times 10^{9}$ /L. If
	resolves to grade ≤ 1 within 28 days, resume at reduced
	dose 250 mg PO BID.
	Dose may be reduced to 200 mg PO BID if recurs at
	reduced dose, but if recurs for a third time, treatment
	should be discontinued.
Grade 4 (<0.5 x 10 ⁹ /L)	Dose interruption until recovery to $\geq 1.0 \text{ x } 10^9/\text{L}$. Re-
	initiate olaparib at 250 mg PO BID. If toxicity recurs at
	grade 4: temporary dose interruption until recovery to
	$\geq 1.0 \text{ x } 10^9/\text{L and r}$
Febrile neutropenia	
Grade 3 ANC $<1.0 \times 10^9$ /L with a	Dose interruption until improvement of ANC $\geq 1.0 \times 10^{9}$ /L
single temperature of >38.3 °C (101	and no fever. Restart with dose reduction of 250 mg PO
°F) or a sustained temperature of \geq 38 °C (100.4 °F) for more than one hour	BID. If febrile neutropenia recurs, discontinue olaparib.
Grade 4 Life-threatening	Discontinue olaparib
consequences; urgent intervention	
indicated	
multated	

Treatment-related anemia may be managed by transfusions without interruption of treatment Any hematologic AE that does not resolve to grade ≤ 1 within 28 days despite maximum supportive care remove from study.

For severe hematologic toxicity or in cases where blood transfusion is still required despite dose reductions, interrupt olaparib and initiate appropriate hematologic investigation. If blood parameters remain clinically abnormal after 4 weeks of dose interruption, bone marrow biopsy and cytogenetic analysis should be considered.

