6.2.2. Supportive care

No routine prophylactic medications are indicated at the start of therapy. In general, the use of any concomitant medication/therapies deemed necessary for the care of the patient are allowed with the exceptions noted in 6.2.1

6.3. **Duration of Therapy**

Patients will be enrolled continuously to the study. Patients will continue evaluation and treatment until one of the following criteria applies:

- Disease progression per RECIST v1.1³⁹
- Unacceptable adverse event(s) defined as any grade 3 or 4 adverse event, per National Cancer Institute's Common Terminology Criteria for Adverse Events (CTCAE) v5.0 or PRO-CTCAE, that does not resolve to grade ≤ 1 within 28 days after onset.
 - Treatment will be interrupted for any grade 3 or 4 event related to treatment. If the toxicity resolves entirely or to grade 1, treatment will be restarted with a dose reduction. If the event does not resolve within 4 weeks or if two previous treatment interruptions with subsequent dose reductions occur, the patient will be withdrawn.
- Patient withdraws consent.
- Development of second malignancy (except for basal cell carcinoma or squamous cell carcinoma of the skin) that requires treatment, which would interfere with this study.
- Intercurrent illness that prevents further administration of treatment
- General or specific changes in the patient's condition render the patient unacceptable for further treatment in the judgment of the investigator.

6.4. **Duration of Follow Up**

Patients will be followed until the initiation of the next therapy post olaparib treatment. Each patient, regardless of reason for removal from study, will have at least 18 months follow up relative to time of enrollment. Secondary efficacy endpoints will be tracked after official follow-up has been completed.

Assessments in follow up:

- Office visit or review of medical records every 3 months
- Survival endpoints both progression free survival (PFS) and overall survival (OS)

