11. STUDY CALENDAR

Baseline evaluations are to be conducted within 14 days prior to start of trial. Imaging CT scans and x-rays must be done ≤ 4 weeks prior to the start of therapy.

Procedure/Test	Pre- Study	Surveillance every 4 weeks	Day 1 of each cycle	Every 12 weeks	30 day follow- up*	Every 3 months
Informed consent	Х					
Demographics	Х					
Concurrent medications	Х	Х	Х		Х	
Medical history	Х					
Physical exam ^A	Х	Х	Х		Х	
Vital signs ^A	Х	Х	Х		Х	
Height and Weight ^A	Х	Х	Х		Х	
Performance status ^A	Х	Х	Х		Х	
CBC w/diff, platelets A	Х		Х		Х	
Serum chemistry A,B	Х		Х		Х	
CA125 ^A	Х	Х	Х		Х	
PTT/PT/INR ^C	Х					
EKG ^C	Х					
Tumor Measurements D	Х			Х		
Baseline signs & symptoms	Х					
Adverse event evaluation ^E	Х	Х	Х		Х	
Worry and Distress Measures ^F	Х	Х	Х		Х	
Quality of Life and Physical Function Measures ^G	Х			Х	Х	
Financial Toxicity Measures ^H	Х			Х	Х	
Urine or serum B-HCG for WOCBP ¹	X					
Tissue Collection ^J	Х				Х	
PK plasma sample ^K			ХК			

BRCA testing ^L	X			
Survival Follow-up ^M				Х

*Patients should be seen 30 days after completion of treatment to assess for resolution of toxicity

- A. These procedures do not need to be repeated in cycle 1 if done pre-study within 7 days prior to start of protocol therapy.
- B. Albumin, alkaline phosphatase, total bilirubin, direct bilirubin, bicarbonate, BUN, calcium, chloride, creatinine, glucose, potassium, total protein, SGOT [AST], SGPT [ALT], sodium, magnesium, phosphorus
- C. Required pre-study, then as clinically indicated
- D. Prior to olaparib initiation, imaging will only be done for doubling of nadir CA125 or per physician discretion for patient symptoms. Following initiation of olaparib, CT scans will be obtained every 12 weeks as part of surveillance. CT scans can be obtained for rising CA125 or physician preference for patient symptoms before scheduled routine surveillance.
- E. Adverse event evaluation will include both the CTCAE and the PRO-CTCAE (See Appendix D).
- F. Worry and distress measured via Assessment of Survivor Concerns (ASC) (See Appendix E) worry subscale and Impact of Event Scale (IES-R) (See Appendix F).
- G. Health-related quality of life will be measured via The Functional Assessment of Cancer Therapy + Ovarian-specific scale (FACT-O) (See Appendix G) and physical function assessed through the PROMIS Physical Function-20a assesses self-reported performance of physical activities (See Appendix H).

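### The transfusion note under the section 7.1 table has no grade limit, so at grade 3 or 4 anemia it contradicts the anemia rows and section 6.3, and nothing says which rule governs

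*Combined protocol and SAP*

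**What the plan says.** Four parts of the combined protocol and SAP bear on olaparib dosing during anemia.

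- **Anemia rows of the hematologic table (sections 7 and 7.1).** Grades 1 and 2 (hemoglobin 8.0 g/dL or more) need no dose adjustment. Grade 3 (below 8.0 g/dL) and grade 4 both call for "Dose interruption until recovery to grade" 1 or lower. If that is reached within 28 days, olaparib resumes at 250 mg twice daily, with a further step to 200 mg on recurrence and discontinuation on a third occurrence.
- **Section 6.3.** "Treatment will be interrupted for any grade 3 or 4 event related to treatment". Restart requires resolution, or improvement to grade 1, and is at a reduced dose.
- **Note under the table (section 7.1).** "Treatment-related anemia may be managed by transfusions without interruption of treatment". The sentence after it takes off study any patient whose hematologic event has not reached grade 1 or lower "within 28 days despite maximum supportive care remove from study".
- **Next paragraph of section 7.1.** "For severe hematologic toxicity or in cases where blood transfusion is still required despite dose reductions, interrupt olaparib", and start a hematologic work-up.

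**The concern.** The note is a dosing permission for every treatment-related anemia. The rows directly above it and section 6.3 impose the opposite duty at grade 3 and 4, and neither makes an exception for a patient who is transfused. No sentence ranks the rules. Two investigators could therefore manage the same patient in opposite ways, one holding olaparib and one continuing it, and each could cite the protocol.

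What is at stake is patient safety at a defined threshold. An investigator who relies on the note at hemoglobin below 8 g/dL could leave out the interruption and, with it, the dose reduction. The event is expected: section 8.1 lists grade 3/4 anemia at 7% to 21%, and section 3.1.7 admits patients at 8 g/dL, with transfusion allowed to reach it.

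**Working it through.** The check is mainly textual. The plan gives no figure of its own to reproduce here.

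**Step 1. The rules side by side.**

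| Anemia grade | Table rows | Section 6.3 | Note, read literally |
|---|---|---|---|
| 1 and 2 (8.0 g/dL or more) | No dose adjustment | Interruption rule not triggered | Transfuse, continue olaparib |
| 3 (below 8.0 g/dL) | Interrupt to grade 1 or lower, resume at 250 mg twice daily | Interrupt if related | Transfuse, continue olaparib |
| 4 | As grade 3 | Interrupt if related | Transfuse, continue olaparib |

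The texts agree in the first row and contradict each other in the other two.

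**Step 2. Does the next paragraph settle it?** Its first trigger is severe hematologic toxicity. That points towards interruption, most clearly at grade 4, but the word is tied to no grade and the paragraph does not say that it limits the note. Its second trigger is transfusion still needed after dose reductions. In the anemia rows a reduction comes only after an interruption, so an investigator who used the note to avoid interrupting may never reach that trigger.

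**Step 3. Do the stopping rules catch the case?**

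- The removal rule depends on failure to reach grade 1 or lower within 28 days. Grade 1 starts at 10.0 g/dL. If transfusion lifts the patient from below 8.0 to 10.0 g/dL or more in that time, the rule is not met.
- Section 6.3 also says that "if two previous treatment interruptions with subsequent dose reductions occur, the patient will be withdrawn". If olaparib was never interrupted, nothing is counted towards that limit.

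**Step 4. The dosing difference for a patient transfused back to grade 1.** Under the table, olaparib is withheld until recovery and then given at 2 × 250 = 500 mg per day. Under the note, it continues at 2 × 300 = 600 mg per day. The difference is the doses withheld before recovery, plus 100 mg per day afterwards.

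**Step 5. How many patients could meet the conflict.** The inputs are 75 evaluable patients (sample size section, numbered 13.2, within section 14) and the 7% to 21% rate of grade 3/4 anemia (section 8.1).

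- Lower: 75 × 0.07 = 5.25
- Upper: 75 × 0.21 = 15.75

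That is about 5 to 16 patients.

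**The case against.** The strongest reply is that the texts have a sensible joint reading. The note is general and permissive, whereas the rows are specific to grade and section 6.3 is mandatory. A general permission does not naturally cancel two specific duties. The note also has real work to do at grade 2: it says that needing a transfusion is not in itself a reason to hold olaparib. The next paragraph fits this reading, because it treats transfusion need that persists after dose reductions as the point at which to interrupt. An investigator who dosed through grade 3 anemia would have to set aside the rows and section 6.3. In addition, safety issues and protocol deviations are reviewed monthly (section 13.2.1).

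Much of this stands. Confining the note to grade 2 or lower is probably what was intended, and monthly review limits how long a misreading could last. But the reader has to supply the limit. The note follows straight after the rows, so it can equally be read as an exception to them, and that is the unsafe reading.

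Two stronger inferences are tempting and do not hold.

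- **That the note also waives the extra blood counts.** It speaks only of interruption. "Monitor hemoglobin weekly until recovery" is a separate instruction in the grade 3 and 4 rows, and the note does not displace it. The study calendar sets the routine counts and does not cancel those that the table triggers.
- **That a patient could take a full 28 days of doses against the table and then also escape removal.** A full 28 days of excess dosing requires hemoglobin below 10 g/dL throughout, and that patient meets the removal rule. The patient who escapes removal has recovered to grade 1 in time, and the table would then also allow olaparib again, at 250 mg. The two cannot hold for the same patient.

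**Conclusion.** The point holds as a conflict between written safety rules at grade 3 and 4 anemia. It is more than missing detail, because the literal texts give opposite instructions, and it should be corrected. The supported consequence is a possible omission of the interruption and of the dose reduction tied to it, with the patient remaining on 300 mg twice daily if transfusion restores grade 1 within 28 days.

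The range of 5 to 16 patients assumes that all 75 evaluable patients start olaparib and that the listed rates apply to them. A reader might take it as the number who would be mismanaged. The documents do not support that: they give no basis for estimating how often the note would be followed over the rows. The consequence also assumes that hemoglobin reached by transfusion counts as recovery. The protocol does not say otherwise, and the removal rule judges resolution with supportive care in place.

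Nothing here bears on the design, the time-to-next-therapy endpoint, the sample size or the analysis.

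**What to change.** Replace the note with wording that carries the grade limit, for example:

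> *Anemia of grade 2 or lower that is related to treatment may be transfused while olaparib continues, unless transfusions are still needed after dose reductions (see next paragraph). For grade 3 or 4 anemia, transfuse as needed and interrupt olaparib as the table directs.*

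This keeps the legitimate use of the note and makes clear that at grade 3 or 4 transfusion accompanies the interruption and does not replace it. The table, section 6.3 and the next paragraph can then stay as they are. The cost is a wording amendment to one note.

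### Section 7.1 restarts olaparib after grade 4 neutropenia at a neutrophil count that the note under the table and section 6.3 still treat as unresolved

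*Combined protocol and SAP*

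**What the plan says.** All counts are ANC × 10⁹/L. The hematologic table in section 7.1 defines grade 1 as 1.5 or more, grade 2 as 1.0 to below 1.5, grade 3 as 0.5 to below 1.0, and grade 4 as below 0.5.

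- **Grade 3 ANC row.** Treatment is held until ANC is at least 1.0. The next sentence resumes it at a reduced dose if the event "resolves to grade ≤ 1 within 28 days, resume at reduced".
- **Grade 4 ANC row.** Treatment is held until ANC is at least 1.0. The restart instruction follows directly ("initiate olaparib at 250 mg PO BID. If toxicity recurs at"), with no grade 1 condition and no 28-day limit.
- **Grade 3 febrile neutropenia row.** Treatment is held until ANC is at least 1.0 and there is no fever, then restarted at a reduced dose.
- **Note under the table.** "Any hematologic AE that does not resolve to grade ≤ 1 within 28 days despite maximum supportive care remove from study".
- **Section 6.3.** For any treatment-related grade 3 or 4 event: "If the toxicity resolves entirely or to grade 1, treatment will be restarted with a dose reduction". The patient is withdrawn if the event does not resolve within 4 weeks.
- **Section 6.1 and the synopsis.** Both define intolerable toxicity as a grade 3 or 4 event that has not come down to grade 1 or cleared by 28 days after onset.

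**The concern.** Two recovery levels are in force for the same laboratory value. The grade 4 ANC row and the grade 3 febrile neutropenia row use 1.0. The note and sections 6.1 and 6.3 use grade 1, which the table sets at 1.5. The grade 3 ANC cell contains both.

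Nothing in the protocol says whether the row or the general rule prevails. Two investigators who each follow the text could manage the same count in opposite ways: one continues olaparib, the other takes the patient off. That is a patient-safety matter. It also makes treatment exposure and recorded reasons for discontinuation depend on which passage was consulted.

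**Working it through.** No power or sample-size figure is involved. The check sets each rule against the table's own grade bands, for a patient whose ANC has recovered to between 1.0 and just under 1.5 (grade 2).

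| Rule | Count needed to restart | At ANC 1.2 before day 28 | At ANC 1.2 on day 28 |
|---|---|---|---|
| Grade 4 ANC row | 1.0 | restart | already restarted |
| Grade 3 febrile neutropenia row | 1.0, no fever | restart | already restarted |
| Grade 3 ANC row | hold ends at 1.0; resume at 1.5 | hold over, not resumed | resume condition not met |
| Note under the table | – | no action yet | remove, if supportive care has been maximal |
| Section 6.3 | grade 1, i.e. 1.5 | do not restart | withdraw |

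**Grade 4 event.** Suppose ANC reaches 1.2 on day 14 and is still 1.2 on day 28. The row has the patient back on drug from day 14. Section 6.3 would not have allowed that restart, and on day 28 the note and 6.3 both end participation. The conflict covers the whole band from 1.0 to below 1.5.

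**Grade 3 febrile neutropenia.** The row gives the same restart at 1.0. The table lists only grades 3 and 4 for this event, so it could be called resolved once fever has gone. The count itself is still a grade 2 ANC value and meets the note on that footing.

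**Grade 3 ANC event.** The resume condition, the note and 6.3 agree on grade 1. The mismatch is inside the cell: between 1.0 and 1.5 the hold has ended but resumption is not permitted. The anemia and thrombocytopenia rows use grade 1 or better for both steps, so this mismatch is specific to neutrophils.

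**Ordering.** By the rows alone, restart needs 1.5 after grade 3 and 1.0 after grade 4.

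**Size.** Section 8.1 lists grade 3/4 ANC decrease in 7% to 11% of patients. With 75 treated:

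- 75 × 0.07 = 5.25
- 75 × 0.11 = 8.25

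So about 5 to 8 patients would enter the grade 3 or 4 ANC rows. This is a ceiling on the number exposed to the conflict. The documents do not split grade 3 from grade 4 and give no recovery times.

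**The case against.** The best defence is that section 6.3 already states one restart level for every treatment-related grade 3 or 4 event, and that the table column is headed as recommendations. On that reading the general rule governs and the grade 4 row is loose wording. But no precedence is stated, and the row gives its own explicit threshold followed at once by re-initiation. Staff working from the table would restart at 1.0.

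A second defence is that the grade 4 ANC row is incomplete in the available text. It breaks off within the recurrence instruction, which begins "grade 4: temporary dose interruption until recovery to". The first-occurrence instruction is complete before that point, and the conflict rests only on it.

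Some stronger readings are tempting but not supported:

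- *One patient is at once resumed, not resumed and removed.* No single event falls under both the grade 3 and grade 4 rows. For grade 3 the resume rule, the note and 6.3 agree.
- *The note removes anyone above grade 1.* It applies only after 28 days and only when supportive care has been maximal.
- *Removal for neutropenia shortens the primary endpoint.* Under section 1.1 the endpoint ends when post-olaparib treatment starts, not when olaparib stops. Section 6.4 follows patients to next therapy, with at least 18 months from enrollment whatever the reason for removal. An effect is possible, but neither its direction nor its size can be derived.
- *Five to eight patients are affected.* That is the number who might enter the rows, not the number who would sit between 1.0 and 1.5 at day 28.

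**Conclusion.** The inconsistency is real. For grade 4 neutropenia, the row's restart at 1.0 contradicts section 6.3's restart level, and for a patient still below 1.5 at day 28 it contradicts both the note and 6.3. The grade 3 febrile neutropenia row restarts at the same count and needs the same reconciliation. The grade 3 ANC cell is a separate, smaller defect, a hold level that differs from its own resume level.

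The size is limited. The ceiling of about 5 to 8 assumes that all 75 patients receive olaparib and that the section 8.1 range applies to them. The number actually caught is unknown and may be smaller. The case for changing the text is patient safety and uniform conduct, not a demonstrated bias in time to next therapy. No view is taken on which threshold is clinically right.

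**What to change.** Reconcile the grade 3 and grade 4 ANC rows, the grade 3 febrile neutropenia row, the note under the table, and sections 6.1 and 6.3, so that they state one recovery level and one consequence at day 28. The synopsis repeats the section 6.1 definition and should be kept in line. If the investigators intend a row to be an exception to the general rule, the text should say so and state which passage prevails. The choice of level is theirs.

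The cost is a wording amendment. Sample size, endpoints and analysis do not change.

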7.2.1. Nausea/vomiting

Prompt treatment of mild/moderate nausea/vomiting with antiemetics. If not controlled with medication, interrupt olaparib treatment; when symptoms are grade 1, restart olaparib treatment per protocol.

